12.1. Extent of Exposure

The extent of exposure will be summarized by the number of doses received, the number of cycles completed, and dose received in milligram/kilogram. A cycle is considered completed if the patient received all treatment infusions required during a given cycle.

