 22. Patients with hereditary problems of galactose intolerance, including Lapp lactase deficiency or glucose-galactose malabsorption

TRC105 investigational product dose and mode of administration:**Phase 1b:**

Dosing will begin at 8 mg/kg (cohort 1); however a -1 cohort has also been included (6 mg/kg) and will be enrolled if 8 mg/kg is found to exceed the MTD. Following the appropriate premedication regimen, the first weekly TRC105 dose (cycle 1 day 1) will be split into two doses whereby 3 mg/kg is administered on cycle 1 day 1 and the balance (e.g., 5 mg/kg for Dose Level 1) is administered on

cycle 1 day 4. Thereafter, the TRC105 dose will be administered i.v. weekly during each 28-day cycle.

In cohort 3 (10 mg/kg weekly during cycle 1; 15 mg/kg every two weeks beginning with cycle 2 day 1) and cohort 4 (10 mg/kg weekly during cycle 1; 20 mg/kg every two weeks beginning with cycle 2 day 1) the first weekly TRC105 dose will also be split into two doses whereby 3 mg/kg is administered on cycle 1 day 1 and the balance is administered on cycle 1 day 4. Starting on cycle 2 day 1 and beyond, TRC105 will be administered every two weeks on days 1 and 15.

Phase 2:**Weekly Dosing:**

Following the appropriate premedication regimen, TRC105 is to be administered intravenously over 1 to 4 hours on days 1 (3 mg/kg), 4 (7 mg/kg), 8 (10 mg/kg), 15 (10 mg/kg) and 22 (10 mg/kg) of cycle 1 and 10 mg/kg on days 1, 8, 15, and 22 of subsequent 28 day cycles.

Every Two Week Dosing:

TRC105 10 mg/kg weekly during cycle 1 as described above. Starting on cycle 2 day 1 and beyond, TRC105 may be administered every two weeks on days 1 and 15 at either 15 mg/kg or 20 mg/kg based on the every two week dosing MTD determined in Phase 1b (Cohort 3 & 4).

Axitinib dose and administration:

Axitinib will be initially dosed orally at its approved dose of 5 mg p.o. BID daily.

Duration of treatment:

Patients are eligible for treatment until disease progression, unacceptable toxicity or withdrawal of consent, or other reasons. Phase 1b patients may be withdrawn for DLT, but DLT does not mandate withdrawal if the DLT resolves and can be treated (i.e., a first dose infusion reaction). A patient should be withdrawn from study treatment if, in the opinion of the Investigator, it is medically necessary, or if it is the wish of the patient. In addition, patients will be withdrawn from treatment in the case of:

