11. **Axitinib Dosing:** Oral axitinib will be dosed twice daily on days 1-28 of each 28 day cycle according to the axitinib package insert. Patients who tolerate the starting dose with no adverse reactions above grade 2 for four weeks will have the axitinib dose increased. See [Section 6.2](#) for specific dosing guidelines.
12. **Imaging:** CT or MRI scans of chest, abdomen, and pelvis with contrast to be performed at screening, and on-study as outlined in the assessment table. If subjects are unable to receive CT contrast due to CT contrast medium allergy or renal insufficiency, enhanced MRI scans may be used. A combination of non-contrast CT and MRI studies (such as chest CT without contrast and abdominal MRI with contrast) may be used. The same method of assessment must be used throughout the course of the study thereafter. Similarly, if a subject develops a contraindication to CT contrast during the course of the study; assessments may shift to non-contrast CT of the chest and contrast-enhanced MRI of the abdomen for subsequent scans. In addition, a brain MRI or CT with contrast to be performed at screening to assure absence of CNS metastases and on study as needed if metastases are suspected. Bone scans are to be performed at screening and throughout the study at the time of CT assessments if bone metastases are present and cannot be followed by CT. Known areas of disease should be consistently followed throughout the study. Assessments should be performed whenever disease progression is suspected. Allowable window for tumor imaging studies is +/- 7 days. Scans will be performed every 56 days from the date of randomization.

-
13. **12-Lead ECG:** Single tracing 12-lead ECG will be performed at screening and at time points indicated in the Schedule of Assessments (pre-dose). For a QTc >500 ms, a repeat ECG for confirmation and evaluation of the ECG by a cardiologist is recommended. Additional ECGs may be performed on study as clinically indicated.
 14. **Concomitant Medications and Treatments:** Concomitant medications and treatments will be recorded from 28 days prior to the start of study treatment and up to 28 days following the last dose of study treatment.

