6.5. Patient Enrollment

Patients will be manually enrolled by TRACON Pharmaceuticals and assigned an eight digit patient number. This eight digit number will be used to identify patients throughout their participation in the trial. For the phase 2 portion of the study patients will also be assigned to Arm A (axitinib therapy alone) or Arm B (TRC105 + axitinib). A regulatory binder will be provided and will include detailed instructions for the manual enrollment process.

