Concomitant Treatment	Start Date	First of Month	Jan 01 of Year
	Stop Date	Last day of Month	Dec 31 of Year
Informed Consent Reconsent	Date of Consent/Reconsent	Last day of Month	Dec 31 of Year
Medical History and Baseline Emergent AE	Start Date	First of Month	Jan 01 of Year
	Stop Date	Last day of Month	Dec 31 of Year
Primary Diagnosis	Date of Diagnosis	Last day of Month	Dec 31 of Year
Prior Cancer Surgery	Date of Surgery	Last day of Month	Dec 31 of Year
Prior Cancer Therapy	Start Date	First of Month	Jan 01 of Year
	Stop Date	Last day of Month	Dec 31 of Year
	Date of Progression on Therapy	Last day of Month	Dec 31 of Year
Prior Radiation Therapy	Start Date	First of Month	Jan 01 of Year
	Stop Date	Last day of Month	Dec 31 of Year
Demography	Birth Date	15 th of the Month	Jun 15 of Year

8. Patient Accountability and Patient Disposition

The number enrolled, the number of doses received and the number of cycles completed (per Section 12.1) will be presented for each dose level for the phase 1 portion and by treatment group for the phase 2 portion. A summary of reasons for withdrawal will be provided. The number of patients in the safety populations will also be presented. Patient disposition, including reasons for discontinuation, and number of cycles completed will be listed.

9. Demographics and Baseline Characteristics

Demographics and baseline characteristics will be summarized by dose level. Demographic variables, including age, gender, and race will be summarized in a tabular form.

Initial diagnosis, prior cancer surgery, prior radiotherapy, prior cancer therapy, and medical history will be listed. Initial diagnosis, prior cancer surgery, prior radiotherapy, and prior cancer therapy will also be summarized by dose level for the phase 1 portion and by treatment group for the phase 2 portion.

10. Concomitant Medications and Treatments

A listing of all concomitant medications and treatment will be provided by patient, drug name, start and stop dates, whether the medication or treatment was ongoing. Concomitant medications will be coded by using WHO Drug Dictionary version September 2012.

11. Efficacy Endpoints

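### Cycle completion is defined by infusions alone, so the Phase 2 counts of completed cycles cannot be compared between arms

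*SAP*

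**What the plan says.** SAP Section 12.1 names three exposure measures: "The extent of exposure will be summarized by the number of doses received, the number of cycles completed, and dose received in milligram/kilogram". It then defines the second of them: "A cycle is considered completed if the patient received all treatment infusions required during a given cycle". Oral dosing is not mentioned, and neither document gives another rule for cycle completion.

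SAP Section 8 carries the definition into the disposition summary by explicit cross-reference. There, "the number of doses received and the number of cycles completed (per Section 12.1) will be presented for each dose level" in the Phase 1 portion and "by treatment group for the phase 2 portion".

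In Phase 2, Arm A is axitinib alone. Its schedule (Protocol Table 9) has no infusion row, and the dosing footnote reads: "Oral axitinib will be dosed twice daily on days 1-28 of each 28 day cycle according to the axitinib package insert". Arm B adds TRC105 infusions, which in cycle 1 fall on "days 1 (3 mg/kg), 4 (7 mg/kg), 8 (10 mg/kg), 15 (10 mg/kg) and 22 (10 mg/kg) of cycle 1" (Protocol Synopsis).

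**The concern.** The rule works where every patient receives infusions, as in Phase 1b. In Phase 2 it is applied to a randomised comparison in which one arm has none.

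A reader of the by-arm table would take cycles completed as a measure of how much treatment each arm received. Under the stated rule, the Arm A figure carries no information about axitinib intake, and the Arm B figure carries information about TRC105 only. A lower Arm B count could be read as poor tolerability of the combination, and axitinib interruptions in the control arm would not show in this count.

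The same section's dose measure, mg/kg, has a related problem. Axitinib is given as a fixed dose in mg (Protocol Section 6.2.2), so that measure has no meaning for Arm A and covers only one of the two drugs in Arm B.

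**Working it through.** The documents state no figure for this point, so there is none to reproduce. The check applies the rule to each arm's schedule.

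**Infusions required per cycle, k**

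- Arm A, every cycle: k = 0 (Protocol Table 9).
- Arm B, cycle 1: k = 5 (days 1, 4, 8, 15 and 22; Protocol Synopsis).
- Arm B, later cycles on the weekly schedule: k = 4 (days 1, 8, 15 and 22; Protocol Synopsis).
- Arm B, later cycles on the every-two-week schedule: k = 2 (days 1 and 15; Protocol Synopsis).

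**Arm A.** With k = 0, the condition that all required infusions were received is met automatically, so on the literal reading every started cycle is completed at any axitinib intake. The case can arise in practice. Protocol Section 6.2.6 provides for axitinib interruption, and Protocol Section 5.2 withdraws an Arm A patient only when axitinib has been held for more than 8 consecutive weeks. Since 8 × 7 = 56 days = 2 × 28 days, up to two whole cycles without drug could count as completed. A programmer might instead code Arm A as zero or as not applicable. The SAP does not choose between these, and none of the three is comparable with Arm B.

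**Arm B.** One missed infusion out of 5, 4 or 2 makes that cycle not completed, whatever axitinib was taken. For patients who continue on axitinib alone (Protocol Sections 5.2 and 6.1.7) the rule is ambiguous. If infusions are still regarded as required, no later cycle is completed; if they are not, every later cycle is.

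**Illustration of size.** Let m be the chance that any one infusion is missed, independently of the others. The documents do not give m, so it is assumed and shown over a range. Then P(cycle completed) = (1 − m)^k.

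| | m = 2% | m = 5% | m = 10% | m = 20% |
|---|---|---|---|---|
| Arm A, k = 0 (literal reading) | 1 | 1 | 1 | 1 |
| Arm B cycle 1, k = 5 | 0.90 | 0.77 | 0.59 | 0.33 |
| Arm B later weekly cycle, k = 4 | 0.92 | 0.81 | 0.66 | 0.41 |
| Arm B later every-two-week cycle, k = 2 | 0.96 | 0.90 | 0.81 | 0.64 |

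Over four cycles on treatment, the expected number completed is (1 − m)^5 + 3(1 − m)^k, with k = 4 or 2. At m = 5% on the weekly schedule this is 0.7738 + 3 × 0.8145 = 3.22.

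| Expected completed, of 4 | m = 2% | m = 5% | m = 10% | m = 20% |
|---|---|---|---|---|
| Arm A (literal reading) | 4 | 4 | 4 | 4 |
| Arm B weekly | 3.67 | 3.22 | 2.56 | 1.56 |
| Arm B every two weeks from cycle 2 | 3.79 | 3.48 | 3.02 | 2.25 |

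Time on treatment is the same in every row, so the gap between arms comes from the definition alone.

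**The case against.** Section 12.1 reads as text written for TRC105: it speaks of infusions and of mg/kg. On a natural reading the measure is simply not applicable to Arm A, and the SAP nowhere says that Arm A cycles are all complete. This stands in part. The 100% figure is the literal reading, not a stated result. But Section 8 sends the measure to both treatment groups by cross-reference without making an exception for Arm A, so the Arm A entry still has to be filled in somehow.

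Axitinib exposure is also reported elsewhere. The Phase 2 by-arm tables include 14.1.4 for TRC105 and 14.1.5 for axitinib, and Listings 16.2.5.1 and 16.2.5.2 give the dosing records. This stands too, and it limits the damage. However, neither table comes with its own cycle rule, and neither corrects the Section 8 summary.

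Three stronger readings might be inferred, and the documents do not support them:

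- That an Arm B patient who misses one infusion completes no cycles. The rule works cycle by cycle, so only the affected cycle fails.
- That a formal between-arm comparison is invalid. The SAP only presents these counts by group and names no test for them.
- That the safety or efficacy conclusions are distorted. SAP Section 12.2 summarises adverse events as numbers and percentages of patients, not per completed cycle, and PFS does not use the count.

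Finally, scoring both arms on axitinib alone would not be a sound repair. Arm B patients may continue on TRC105 alone (Protocol Sections 5.2 and 6.2.6), and they would then be shown as completing no further cycles.

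**Conclusion.** The point holds as a defect in a descriptive measure. Followed as written, cycles completed is vacuous or undefined in Arm A and depends only on infusions in Arm B, so the by-arm figures are not comparable. That conclusion rests on the text and needs no assumption.

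The numerical size does rest on assumptions: the literal reading for Arm A, an independent chance of missing each infusion that the documents do not give, and four cycles on treatment in each arm. For miss rates from 2% to 20%, the artificial gap is 0.33 to 2.44 cycles out of 4 on the weekly schedule (4 − 3.67 and 4 − 1.56). On the every-two-week schedule it is 0.21 to 1.75 (4 − 3.79 and 4 − 2.25).

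The consequence is minor. It reaches only the disposition and exposure summaries, and the separate exposure tables and dosing listings still report each drug.

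**What to change.** For Phase 2, revise SAP Sections 8 and 12.1 as follows:

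- Define cycle completion separately for each drug. For TRC105, in Arm B only, report infusions given out of infusions planned. For axitinib, in both arms, state a criterion based on dosing-log intake over the 28-day cycle.
- Use cycles started, or time on treatment, as the common by-arm measure in the Section 8 summary.
- Report axitinib exposure in mg or as relative dose intensity, and keep mg/kg for TRC105.

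No new data are needed. Patients already keep an axitinib dosing log that is reviewed before each cycle (Protocol Section 6.4.2), drug accountability is done at the start of each cycle (Protocol Section 6.2.7), and both dosing records are listed. The cost is slightly more programming and the need to choose and state one axitinib intake criterion for the analysis.

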12.2. Adverse Events

All AEs with an onset after initiation of treatment will be considered as treatment-emergent AEs. A preexisting condition that worsens during the treatment period will also be considered as a treatment emergent AE. All AEs will be coded by system organ class (SOC) and preferred term using NCI CTCAE (MedDRA) version 4.0.

The number and percentage of patients with the following types of treatment-emergent AEs will be summarized for each study arm: common and serious AEs, AEs related to study medication, AEs resulting in study discontinuation, and clinically significant laboratory abnormalities. Laboratory data will be summarized for baseline, treatment visits and change from baseline as appropriate for each arm. Non-treatment-emergent serious AEs will be described separately. Deaths will be reported with demographic information. Comparison of categorical values will be made by Chi-square or Fisher exact test and of continuous variables will be made by Student t test.

For the phase 1b portion treatment-emergent AEs will be summarized by dose level. For the phase 2 portion treatment emergent AEs will be summarized by treatment group. Treatment-emergent is defined as all events starting during or after the first dose of study drug (or axitinib) until 28 days following the last dose of study drug or axitinib, whichever is later. The number and percentage of patients with AEs will be displayed by SOC and PT. Summaries will be provided of AEs by grade and of AEs by relationship to study medication. Serious AEs, AEs leading to study discontinuation, AEs resulting in dose delay, and AEs with an outcome of death will be summarized and listed.

For the phase 1b portion, a summary table and listing will also be provided for DLTs.

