7. Missed study drug treatment for > 8 consecutive weeks (i.e., both TRC105 and axitinib dosing held if assigned to the combination arm or axitinib held if assigned to axitinib alone arm). However, patients assigned to the combination arm who cannot tolerate axitinib or TRC105 therapy and who demonstrate a response of complete response (CR), partial response (PR) or stable disease (SD) with the combination and are thought to benefit from continued single agent therapy may continue on study on TRC105 or axitinib alone.

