6.2.6. Axitinib Dose Modification

Patients who are intolerant of axitinib may continue TRC105 treatment alone on the study.

Axitinib should be held for two weeks prior and for two weeks following surgical procedures.

Dose reduction is allowed based on individual safety and tolerability. Following dose interruption, axitinib treatment may be reinitiated when the toxicity that prompted dose reduction has resolved to baseline or grade 1. See axitinib package insert in [Section 20.3](#).

All patients will initially receive axitinib 5 mg twice daily; patients randomized to receive TRC105 will receive TRC105 at 3 mg/kg on day 1, 7 mg/kg on day 4, and 10 mg/kg on day 8 and weekly thereafter. Patients **in both arms** who tolerate axitinib for at least two consecutive weeks with no adverse reactions > Grade 1 considered clinically significant (according to the Common Toxicity Criteria for Adverse Events [CTCAE]), will, at the discretion of their treating physician, have the axitinib dose increased to 7 mg twice daily beginning on cycle 2 day 1, unless the patient's blood pressure is > 150/90 or the patient is receiving more than one antihypertensive medication. Subsequently, with the same criteria, patients who tolerate the axitinib dose of 7 mg twice daily for at least two consecutive weeks may have the axitinib dose increased to a maximum of 10 mg twice daily beginning with cycle 3 day 1. Dose reductions of axitinib and TRC105 are allowed per patient tolerance (including to doses of axitinib between 5 and 10 mg twice daily). Reasons for dose reduction and reasons for not increasing the axitinib dose will be documented on the CRF.

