14.3.1.4. Treatment-Emergent Adverse Events by Maximum CTCAE Grade

14.3.1.7. Number (%) of Patients with Serious Treatment-Emergent Adverse Events

14.3.1.8. Number (%) of Patients with Adverse Events Leading to Discontinuation

14.3.3. Narratives of Deaths, Other Serious and Certain Other Significant Adverse Events

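### The AE discontinuation measure means loss of the only drug in Arm A but generally loss of both drugs in Arm B, and AE percentages are compared without regard to exposure

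*SAP*

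**What the plan says.** SAP 12.2 lists the treatment-emergent AE types to be counted in each arm: "common and serious AEs, AEs related to study medication, AEs resulting in study discontinuation, and clinically significant laboratory abnormalities". Further down, the same section adds that "AEs leading to study discontinuation, AEs resulting in dose delay, and AEs with an outcome of death will be summarized and listed", and that "The number and percentage of patients with AEs will be displayed by SOC and PT", with summaries by grade and by relationship. For between-arm testing it says "Comparison of categorical values will be made by Chi-square or Fisher exact test". No alpha is given for these tests.

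The Phase 2 table list (SAP 19.4) has one relevant table, 14.3.1.8, "Number (%) of Patients with Adverse Events Leading to Discontinuation". It does not say what is discontinued: TRC105, axitinib or the study.

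The protocol separates stopping a drug from leaving the study. Section 5.2, item 7, says that combination-arm patients who cannot tolerate one drug, who have CR, PR or SD, and who "are thought to benefit from continued single agent therapy may continue on study on TRC105 or axitinib alone". Section 6.1.7 repeats this. Section 6.2.6 opens more broadly, "Patients who are intolerant of axitinib may continue TRC105 treatment alone on the study", and restates the response condition later. Table 15 provides for a permanent stop of TRC105.

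Treatment continues until progression (Synopsis, Duration of treatment). The AE window closes 28 days after the last dose of either drug (SAP 12.2). SAP 12.1 summarizes exposure as doses, cycles and mg/kg, with no person-time.

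**The concern.** A by-arm comparison needs one definition that means the same in both arms. In Arm A, permanently stopping axitinib for toxicity ends study treatment. In Arm B, a patient can permanently lose either drug to toxicity and still be on study, and so is not a study discontinuation. Item 7 of Protocol 5.2 builds in the same asymmetry: missed treatment leads to withdrawal when axitinib is held in the axitinib-alone arm, but only when both drugs are held in the combination arm.

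The bias favours the combination, on a measure that readers use to judge whether the added drug can be tolerated. Equal axitinib toxicity in the two arms could even look like better tolerability in Arm B.

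The second issue works the other way. If TRC105 delays progression, Arm B patients are at risk of AEs for longer, and a test of crude proportions can then flag an excess that reflects time on treatment alone. The two effects concern different tables and do not cancel.

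**Working it through.** **Design inputs (SAP 4.2).** Hazard ratio 0.67, one-sided alpha 0.10, 80% power, 1:1 allocation, 115 events, about 150 patients (75 per arm), control median PFS 4.8 months, accrual 12 months, minimum follow-up 4.3 months.

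**The plan's own figure.** With z-values 1.2816 and 0.8416, (1.2816 + 0.8416)² = 4.508.
- Schoenfeld: 4 × 4.508 / (ln 0.67)² = 18.03 / 0.1604 = 112.4, so 113.
- Freedman: 4.508 × (1.67 / 0.33)² = 115.5, so 116.

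The stated 115 reproduces, so the design inputs can be used below. The AE section states no figure of its own.

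**Discontinuation.** Let x be the share of Arm B who permanently stop TRC105 for an AE, and f the share of those who stay on axitinib. The study-discontinuation measure shows x(1 − f) and leaves out 75·x·f patients. The documents give neither x nor f; both are assumptions.

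| x | f | Shown | Patients not counted |
|---|---|---|---|
| 10% | 25% / 50% / 75% | 7.5% / 5% / 2.5% | 1.9 / 3.8 / 5.6 of 7.5 |
| 20% | 25% / 50% / 75% | 15% / 10% / 5% | 3.8 / 7.5 / 11.3 of 15 |

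The same arithmetic applies to axitinib. If 20% of each arm stopped axitinib for an AE, Arm A would show 20%, and Arm B 15%, 10% or 5% from that source, depending on how many continued on TRC105.

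**Exposure.** Assumptions: time on treatment T equals PFS and is exponential, with medians 4.8 and 4.8 / 0.67 = 7.16 months; follow-up C is uniform from 4.3 to 16.3 months; the AE window is W = min(T + 0.92, C), where 0.92 months is 28 days; the AE hazard h is constant and the same in both arms. Then P(AE) = 1 − E[exp(−hW)]. Mean windows are 5.8 months (A) and 6.8 months (B). The last two columns give the chance that a two-sided 5% test with 75 per arm declares an Arm B excess (nominal 2.5%), computed exactly from the two binomials.

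| h per month | Arm A | Arm B | Uncorrected chi-square | Fisher |
|---|---|---|---|---|
| 0.02 | 10.8% | 12.5% | 5.2% | 3.2% |
| 0.05 | 24.1% | 27.7% | 7.1% | 5.1% |
| 0.10 | 40.8% | 46.0% | 10.2% | 7.7% |
| 0.20 | 61.5% | 67.3% | 11.1% | 8.2% |

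At a hazard ratio of 1 the two proportions are equal, and chi-square returns 2.5-2.8%. If instead every patient were followed to the end of treatment, an AE seen in 10% / 30% / 50% of Arm A would appear in 13.8% / 38.1% / 59.0% of Arm B at the same hazard.

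**The case against.** Five points on the other side deserve an answer.

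- **The AE is not lost.** A reader might infer that a patient who stops TRC105 and stays on axitinib vanishes from the safety comparison, or that discontinuation is all the SAP tabulates. Neither is so. SAP 12.2 also covers dose delays, deaths, and all AEs by SOC and PT, grade and relationship. Exposure to each drug has its own Phase 2 table (14.1.4, 14.1.5). What is lost is the count as a discontinuation; a dose-delay summary does not capture a permanent stop.
- **Table 14.3.1.8 could be read per drug.** Its title omits the word study. But the SAP 12.2 text says study discontinuation twice, and nothing defines a per-drug reading.
- **Many Arm B toxicity stops will be counted.** Single-agent continuation requires CR, PR or SD and expected benefit. Protocol 5.2, item 6, and Table 16 mandate full withdrawal for several serious toxicities. This limits f, so an illustration in which every single-drug stopper stays on study would be an extreme case.
- **Longer Arm B exposure is not a design feature.** It follows only if TRC105 delays progression, and it would reverse if Arm B stopped earlier. For a rare AE or with Fisher, the inflation is small. SAP section 12 describes the safety analyses as descriptive.
- **Denser Arm B visits.** From cycle 3, AEs and hematology are scheduled on days 1 and 15 in Arm B (Table 10) but on day 1 only in Arm A (Table 9). A reader might infer that AE time goes uncovered in Arm A. The visit question (Protocol 8.3.1) asks about the whole interval since the last visit, and SAP 12.3 reports laboratory results by visit, so a day 1 comparison is already possible.

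These points narrow the concern. They do not supply a discontinuation count that means the same in both arms.

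**Conclusion.** The concern holds in this limited form. As written, the discontinuation comparison is not like for like and understates stopping for toxicity in Arm B. Its size cannot be fixed from the documents. With 20% stopping TRC105 for an AE and 25-75% of them staying on axitinib, the figure shown falls to between 15% and 5%. The direction does not depend on those assumptions as long as some patients continue on one drug.

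The exposure issue is real but conditional. At a hazard ratio of 0.67 the false flag of an Arm B excess rises from 2.5% to about 5-11% for hazards of 0.02 to 0.20 per month. This rests on exponential time on treatment, a constant AE hazard and a two-sided 5% uncorrected chi-square test. It is lower with Fisher and absent at a hazard ratio of 1. It justifies an additional analysis; it does not justify discarding the crude percentages.

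**What to change.** In SAP 12.2 and Table 14.3.1.8, report AEs leading to permanent discontinuation of (a) TRC105, (b) axitinib, (c) either drug and (d) all study treatment. Compare the arms on (b), which is the like-for-like measure, and on (c), which shows how many patients lost part of their assigned treatment.

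Beside the crude AE percentages, add exposure-adjusted rates or time to first AE. Keep the crude percentages. The protocol's background describes infusion reactions and headaches mainly with the first infusion, and epistaxis, gingival bleeding and telangiectasia within the first month (Sections 2.3.2.1 and 2.3.6.1). Dividing such early events by longer Arm B person-time would dilute real harm. For a similar reason, do not confine laboratory comparisons to day 1: that would drop Arm B's day 15 hematology, although anemia is the single-agent dose-limiting toxicity.

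The cost is SAP wording and a few table columns, with no protocol change. Dosing records for both drugs are already listed (Listings 16.2.5.1 and 16.2.5.2). I assume that the CRF links each permanent stop to its AE, which the documents do not show. The combination's discontinuation figure will look less favourable.
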